After GM-CSF's preclinical results described above in models of AD and other neurodegenerative diseases and the association of GM-CSF with improved cognition in bone marrow transplant patients, the pilot safety and efficacy trial was initiated at the University of South Florida (USF), in which sargramostim/Leukine® was administered to mild-to-moderate AD participants for 15 days over a 19-day period (NCT01409915). At USF, the first 14 participants completed the study given placebo or sargramostim at a dosage of 125 $\mu g/m^2/day$ SC, which is half of the FDA-recommended dose. The Data Safety Monitoring Board (DSMB) met and determined that sargramostim was safe, and approved subsequent participants to receive treatment dosage of sargramostim at the full FDA-recommended dose of 250 $\mu g/m^2/day$ SC. Then with the relocation of Drs. [name] and [name] to Colorado, the trial was halted and amended to increase new enrollment to

40 participants (i.e. 20 sargramostim-treatment, 20 placebo treatment). All participants (3 at USF and 37 at CU-AMC) completed the trial either with placebo or at the full FDA-recommended dose of 250 $\mu g/m^2/day$ SC. The only AEs reported have been mild expected reactions to sargramostim, including injection site reactions, such as redness, swelling, itching, and bruising. No drug-related SAEs were reported, including no incidence of amyloid-related imaging abnormalities (ARIAs), indicating vasogenic edema (ARIA-E) and/or microhemorrhage (ARIA-H), which have been observed in all other trials testing anti-amyloid immunotherapy drugs in AD participants.

Final analysis of 40 participants showed a statistically significant treatment effect of sargramostim as assessed by MMSE, but none for the other assessments (ADAS-cog, CDR-SB, ADCS-ADL, TRAILS A).

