9.1 Sample size considerations

As the primary goal of this clinical trial is the safety and tolerability of long-term use of sargramostim in participants with mild-to-moderate Alzheimer's disease, a sample size of 42 participants (28 sargramostim-treated [1250 mcg/m²/ week subcutaneously], and 14 placebo equivalent) is considered sufficient to meet the endpoint of safety and is consistent with the lack of drug related SAEs in our recently-completed randomized, double blind, placebo-controlled trial of sargramostim in 40 (20 sargramostim-treated:20 placebo-treated) subjects with mild-to-moderate Alzheimer's disease.

Based on results for 40 participants at the EOT, 45-day follow-up, and 90-day follow-up in our recently completed sargramostim trial in participants with mild-to-moderate Alzheimer's disease, an effect size of

Mean Treatment Difference in Change from	Total	Number of	Number of		
Baseline to End of Treatment (Day 18)	Number of Patients	Sargramostim Patients	Placebo Patients	Alpha	Power
2	102	68	34	0.05	0.91
4	27	18	9	0.05	0.92
6	12	8	4	0.05	0.92
8	9	6	3	0.05	0.97

Table 1. Model for MMSE Total Score, Assumes no Treatment Effect at Baseline (successful randomization).

around 2–4 was predicted by the MMSE. We believe that the 42 participants (28 sargramostim-treated [1250 μ g/m²/week (178.57 μ g/m²/day subcutaneously seven days a week], and 14 placebo equivalent) who will be recruited for this study will provide sufficient power to allow valid analyses of the secondary and exploratory endpoints. Therefore, at least 42 individuals with mild-to-moderate Alzheimer's disease, age 60–85, of either sex, will be randomized (28 sargramostim participants and 14 placebo participants) for this proposed placebo-controlled study. For effect sizes of 2, 4, 6, or 8 (the expected treatment group differences in change between baseline and follow-up for MMSE total score), **Table 1** shows the number of participants required to achieve 91–97% power. Recruitment and treatment initiation will be timed to allow for the interim assessments before further participants are treated, thus assuring maximum early knowledge of any safety concerns.

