9.2.3 Exploratory Objectives

To assess the effect of sargramostim treatment, as compared to placebo, on clinical progression of in individuals with mild-to-moderate AD.

Well validated neuropsychological assessments will be administered and scored using the standardized scoring methods associated with each of the neuropsychological tests. Analysis of the change in cognition from Baseline to EOT will be measured by the change in scores for the MoCA, ADAS-cog₁₃ total scores, CDR-SB, TMT A, ADCS-ADL score, measures of verbal fluency (lexical and semantic) and the NPI score. Due to the multitude of both the neuropsychological tests and the different time points that these tests are administered, a correction method will be used to counteract the problem of multiple comparisons.

To assess the effect of sargramostim treatment, as compared to placebo, on metabolic activity in different brain regions in individuals with mild-to-moderate AD.

FDG-PET will be used to assess overall metabolic activity in different brain regions, particularly in the medial temporal lobe in potential correlation with changes in MTA, at baseline and at EOT. Standard protocols for 18F-FDG PET imaging studies in conjunction with amyloid PET imaging studies, will be used ^{125, 126}.

To assess the effect of sargramostim treatment, as compared to placebo, on brain amyloid deposition in individuals with mild-to-moderate AD.

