CSF may be collected during screening, and at the EOT visit (i.e. within 2-10 days following the final treatment article injection) for a subset of participants for entry into the study or as part of an optional substudy. A venipuncture blood draw will be performed at each LP procedure visit to obtain serum. Albumin levels will be quantitated within CSF (in mg/dL) and serum (in g/dL) to calculate an Albumin Index (AI). Because albumin is neither synthesized nor metabolized intrathecally, albumin that is found within CSF that is free of blood contamination indicates that the albumin must have come from the plasma through the blood brain barrier (BBB). An AI value < 9 indicates an intact BBB, values 9-14 as slight impairment, values 14-30 as moderate impairment, values 30-100 as severe impairment, and values > 100 as complete breakdown of the BBB 72 . The BBB is known to be impaired in AD $^{131-133}$, and cerebral amyloid angiopathy (CAA), characterized by A β deposition on vessel walls, has been found in over 90% of AD cases 134 . In immunotherapy trials targeting amyloid in the parenchyma and cerebral vascular, the removal of pre-existing vascular amyloid has been attributed to onset of ARIA events (i.e. vasogenic edema and microhemorrhage) 135 , and while we and others have found GM-CSF to quickly reduce

amyloid in transgenic AD models ^{1,68}, no incidences of ARIAs have been observed in the current ongoing sargramostim-AD trial (NCT01409915). GM-CSF is known to induce angiogenesis and restore cerebral blood flow following experimental stroke ^{23, 24, 27, 28}. However, if sargramostim does indeed cause reductions in amyloid deposition over 24 weeks of administration in mild-to-moderate AD participants, evaluating treatment effects on BBB permeability in correlation with MRI safety measures is warranted. Thus, AI values will be calculated at screening and at EOT to assess any treatment-related changes in BBB permeability and to correlate values with any potential trial emergent ARIA events.

To assess the effect of sargramostim treatment, as compared to placebo, on AD-related changes in microstructural white matter measures in individuals with mild-to-moderate AD.

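### Section 9.1 claims sufficient power for the exploratory endpoints, but this is not shown and cannot be derived from Table 1, its only calculation

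*Protocol*

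**What the plan says.** Protocol section 9.1 gives 42 participants (28:14) as enough for the safety objective. It then adds, as the authors' belief, that this number "will provide sufficient power to allow valid analyses of the secondary and exploratory endpoints". The next sentence draws the sample size of at least 42 from that belief.

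The calculation behind it is "Table 1. Model for MMSE Total Score, Assumes no Treatment Effect at Baseline (successful randomization"). According to the text, this table "shows the number of participants required to achieve 91–97% power" for differences of 2, 4, 6 and 8 points. The 4-point row, for example, reads "4 27 18 9 0.05 0.92": 27 participants, 18:9, alpha 0.05, power 0.92. Alpha is 0.05 in every row, and neither the SD nor the sidedness is stated. The expected effect is "around 2–4 was predicted by the MMSE".

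Four other places bear on the exploratory endpoints:

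- **Section 9.2.3, clinical progression.** Because there are many neuropsychological tests and time points, "a correction method will be used to counteract the problem of multiple comparisons". No method is named.
- **Section 9.2.3, blood-brain barrier.** CSF may be collected "for a subset of participants for entry into the study" or in an optional substudy. The amyloid objective likewise describes amyloid PET as an option.
- **Section 2 (LP/PET sequences) and section 6.1.1.** Each participant chooses LP or amyloid PET for entry and the other is optional. Those with a proxy decision maker cannot join the optional sub-studies.
- **Section 4.4.2.** The earlier 40-participant trial found a significant effect on MMSE "but none for the other assessments (ADAS-cog, CDR-SB, ADCS-ADL, TRAILS A").

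**The concern.** Table 1 answers one question: how many participants are needed to detect a given MMSE difference in a single test at alpha 0.05 when everyone contributes. The exploratory endpoints depart from that in three ways:

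- The neuropsychological tests will be judged after a multiplicity correction, so not at the level in Table 1.
- CSF, albumin-index and amyloid PET endpoints will be measured in an unknown fraction of the participants.
- None of the exploratory endpoints has a stated effect or SD, so the MMSE rows cannot be converted to them.

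The stake is interpretation. If section 9.1 stands, a non-significant result on ADAS-cog, CDR-SB, ADCS-ADL, CSF amyloid or SUVR could be presented as negative from an analysis the protocol had called adequately powered. It may simply be uninformative.

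**Working it through.** **Inputs from the protocol.** Section 9.1: 28:14; differences of 2 to 4 points; alpha 0.05; Table 1 rows 68:34, 18:9, 8:4 and 6:3 with power 0.91, 0.92, 0.92 and 0.97. Section 9.2.3: MoCA, ADAS-cog13, CDR-SB, TMT A, ADCS-ADL, NPI and verbal fluency, which is 7 scores, or 8 if lexical and semantic fluency count separately.

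**Assumptions, not in the protocol.** The SD, a two-sided test, Bonferroni as the example correction, subset sizes, and an exploratory effect equal to the MMSE effect in SD units.

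**Step 1: reproduce Table 1.** Normal approximation: power = Φ(δ / [SD·√(1/n₁ + 1/n₂)] − 1.96). With SD = 2.9:

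| Difference | n₁:n₂ | δ/SE | Power | Table 1 |
|---|---|---|---|---|
| 2 | 68:34 | 3.283 | 0.907 | 0.91 |
| 4 | 18:9 | 3.379 | 0.922 | 0.92 |
| 6 | 8:4 | 3.379 | 0.922 | 0.92 |
| 8 | 6:3 | 3.901 | 0.974 | 0.97 |

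Table 1 is therefore consistent with a single unadjusted MMSE test and an SD of about 2.9. A one-sided test with SD 3.2 fits equally well (0.908, 0.922, 0.922, 0.971), so the table does not settle the sidedness.

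**Step 2: MMSE at the planned 28:14.** SE = 2.9 × √(1/28 + 1/14) = 0.949. Noncentral t with 40 df; the two-sided 0.05 critical value is 2.021.

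- 2 points: 2/0.949 = 2.107, power 0.54
- 3 points: 3.160, power 0.87
- 4 points: 4.214, power 0.98

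Under the one-sided reading (SD 3.2) the same calculation gives 0.59, 0.88 and 0.98.

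**Step 3: an exploratory score with the same standardised effect, corrected.** Differences of 2, 3 and 4 points are 0.69, 1.03 and 1.38 SD. The 24-test row is 8 scores × 3 post-baseline visits.

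| Alpha | Critical t | 2 points | 3 points | 4 points |
|---|---|---|---|---|
| 0.05 | 2.021 | 0.54 | 0.87 | 0.98 |
| 0.05/7 | 2.836 | 0.25 | 0.63 | 0.91 |
| 0.05/8 | 2.887 | 0.23 | 0.61 | 0.90 |
| 0.05/24 | 3.292 | 0.14 | 0.46 | 0.81 |

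**Step 4: subset endpoints, no correction.** For an assumed half-size subset of 14:7, SE = 2.9 × √(1/14 + 1/7) = 1.342, with 19 df and critical value 2.093. Power is 0.29, 0.56 and 0.81 at 2, 3 and 4 points. For an assumed 20:10 the 2- and 4-point figures are 0.40 and 0.93; for 8:4 they are 0.17 and 0.53.

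**The case against.** The strongest reply has five parts.

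- **The power might be there.** A reader might infer that the exploratory endpoints are shown to be underpowered. The documents do not support that. Section 9.1 attaches no power figure to them, and at 4 MMSE-equivalent points power is still about 0.90 after Bonferroni over 8 tests. What stands is that the claim is unsupported and, on these assumptions, fails towards the lower end of the protocol's own 2 to 4 range.
- **The problems do not touch every endpoint.** A reader might infer that all exploratory endpoints are corrected and measured in subsets. The correction in section 9.2.3 is worded for the neuropsychological tests and their time points. FDG PET, MRI through end of treatment and blood biomarkers are scheduled for everyone. For those endpoints only the missing effect and SD count against the claim.
- **The earlier trial proves little.** A reader might take its non-significant results on four scales as evidence of smaller effects. Section 4.1 says that trial was short and not powered for efficacy. Those results do not show smaller effects; they only fail to supply a basis for borrowing the MMSE effect.
- **Much of the arithmetic is assumed.** This is true of the SD, sidedness, correction method and subset sizes. The 24-test family is a worst case, since the named endpoints are change from baseline to end of treatment. The figures illustrate the point; it does not depend on them. Table 1 itself contains no arithmetic error.
- **The endpoints are labelled exploratory and a separate SAP will follow.** No decision rule depends on them, and nothing says a null result will be reported as negative. This limits the seriousness. But the sentence is an affirmative claim in the protocol, used to justify 42 participants, and an SAP could not make Table 1 cover these endpoints.

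**Conclusion.** The point holds as an unsupported claim. Sufficient power for the exploratory endpoints is not shown in section 9.1 and cannot be derived from Table 1.

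If an exploratory score shared the MMSE standardised effect, power at 28:14 would run from about 0.23 to 0.90 over 2 to 4 points after Bonferroni over 8. In a 14:7 subset without correction it would run from about 0.29 to 0.81. These ranges rest on an SD of about 2.9 back-solved from Table 1, a two-sided test, and the assumed correction and subset size. A less conservative correction would lose less power.

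The same sentence is also too strong for MMSE at the low end. Table 1 asks for 102 participants to detect 2 points, and 42 give about 0.54 (two-sided).

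**What to change.** In section 9.1:

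1. Limit the power sentence to MMSE and give its power at 28:14 across the 2 to 4 point range: about 0.54 to 0.98 if the test is two-sided. The sponsor should state the sidedness and SD actually used for Table 1, because the table fits more than one choice.
2. Remove the exploratory endpoints from the power claim and add wording such as: *The exploratory endpoints are not powered. They will be reported as estimates with confidence intervals and the number of participants contributing. Any p-values for the neuropsychological tests will carry the correction described in section 9.2.3. A non-significant result will not be read as absence of effect.*

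Both parts are needed. Dropping the exploratory endpoints alone would leave the sentence claiming sufficient power for MMSE even at 2 points.

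The cost is a few sentences in section 9.1, matching reporting language and a less favourable stated claim. There are no extra participants or procedures and no change to the sample size.

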9.2 Data Analysis Plan

9.2.1 Primary Objective: To assess long-term tolerability and safety of sargramostim in individuals with mild-to-moderate Alzheimer's Disease

Generally, descriptive statistics will be utilized to examine safety of participants who received sargramostim injections compared to placebo injections. Safety will be assessed by measuring the toxicity grades of AEs. These toxicity grades have been standardized by the National Cancer Institute (NCI)

Common Toxicity Criteria for Adverse Events (CTCAE Version 5.00: November 27, 2017, attached as Appendix F). Differences in toxicity grades will be compared between treatments using a Wilcoxon test for ordered outcome. MRI scans will be assessed to identify ARIAs, including vasogenic edema and microhemorrhage. Additional safety assessments will include neurological and physical examinations, vital signs and suicidality evaluations. The current study will utilize a Data Safety Monitoring Board (DSMB) to review the clinical data and ensure participant safety within the parameters of the trial.

9.2.2 Secondary Objective: To test the hypothesis that sargramostim treatment, as compared to placebo, slows or halts cognitive decline or improves cognitive function in individuals with mild-to-moderate AD.

The foremost measure used for this secondary endpoint of assessing cognitive function will be the MMSE, as it has been reported to be most sensitive to cognitive changes over time due to treatments in people ranging from late mild cognitive impairment to AD in clinical trials up to 2 years in length ¹²⁴. The cognitive assessment will be based on the participants' MMSE total score changes from Baseline to End of Treatment.

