4.5 Specific Objectives

Improved MMSE change scores in rHuGM-CSF/sargramostim-treated participants compared to placebotreated participants. Mixed model analysis of MMSE data of the completed study of 20 sargramostim-treated participants and 20 placebo-treated participants shows a statistically significant improvement in the sargramostim-treated group at the EOT visit (a) compared to baseline (p=0.074) and to the placebo-treated group (p=0.037), and at the first follow-up visit (45 days post-EOT) compared to the placebo-treated group (p=0.0272) (b). (B) Distribution of delta MMSE scores at the EOT for random groups of 10 sargramostim-treated participants and 10 placebotreated participants. The 20 sargramostim-treated participants and 20 placebo-treated participants were divided into 10,000 random groups of 10 participants each, and the mean Mini-Mental State Exam (MMSE) scores were calculated and graphed as a delta distribution. The mean and median delta was 1.8, as was the delta of the entire 20 sargramostim-treated participants and 20 placebo-treated participants analyzed in (A) showing that the statistically significant difference between the sargramostim-treated participants and the placebo-treated participants at the EOT reflected all parts of the trial.

The specific objectives address two hypotheses: The primary hypothesis is that long-term administration of sargramostim (recombinant human GM-CSF) will be tolerated by and safe for use in participants with mild-to-moderate AD; and the secondary and exploratory hypotheses that sargramostim treatment in participants with mild-to-moderate AD will slow or halt cognitive decline and/or activities of daily living, or improve cognitive functioning and/or activities of daily living,, reduce amyloid load, inhibit progression of medial temporal atrophy (MTA), improve AD-related microstructural white matter changes, improve brain metabolic activity, improve sleep-related measures, improve indices of semantic verbal fluency, and induce changes in peripheral blood and cerebral spinal fluid (CSF) biomarkers toward levels measured in

individuals without dementia. These aims are expressed through primary, secondary and exploratory objectives with related endpoints.

Drimany Objective	Drimany Endnaint

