be assessed for clinical condition by a trial physician or qualified clinician designee AND to then potentially receive new syringes of the study product, which will be provided by the Research Pharmacy (prescribed by the lead clinical sub-Investigator) using procedures designed specifically for these types of unusual circumstances. In contacting and interacting with the study partner and participant for such a scenario, extreme care will be taken to not inadvertently unblind the participant, study partner, or any trial personnel. If unblinding is suspected, provisions described in prior section 7.3 will be followed and a decision will be made by the Sponsor regarding whether to discontinue the participant or to continue with the study.

Dosage Modification Flow Chart

In addition to these key blood values above, the responsible clinician will review the absolute eosinophil value, with a critical value, determined by the hematology specialist, set at $\geq 1.5 \times 10 E3/uL$ as a potential adverse event/clinically significant lab value. Management of this value will be as ongoing AE until the value returns to $< 1.5 \times 10 E3/uL$ and is evaluated by the responsible clinician as not clinically significant. Once the AE is resolved, a subsequent occurrence of an absolute eosinophil $\geq 1.5 \times 10 E3/uL$ will be classified as a new AE. For each new adverse event due to absolute eosinophil values, a symptom check will be conducted using guidelines developed by the hematology specialist. If they are free of symptoms, injections will continue on the regular schedule. If the participant is positive for any symptoms, they will be instructed to hold the injections pending further follow-up by the responsible sub-I. Within each ongoing AE, symptom checks will occur each time the participant's absolute eosinophil count is above the previous high value for that AE.

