7.5 Interruption of Treatment

Temporary interruption of treatment is allowed if a short-term treatment with an excluded medication is necessary, secondary to hospitalization, personal circumstances, or to evaluate the study drug impact on an uncertain AE, including but not limited to abnormal CBC with differential results (see Section 7.4), Grade 2 or higher AEs, and Grade 2 or higher abnormal laboratory values. Interruption of treatment should only be limited to significant events. If temporary interruption is due to an AE, it will be reported to the DSMB as part of the regularly scheduled aggregate reports. In such cases as above, reinitiation of treatment is at the trial physician(s) or qualified delegated clinician(s) judgement.

If a participant has to interrupt treatment for an extended period of time due to a significant medical condition or life event (such as greater than 7 dosing days off drug), it is possible to re-initiate treatment, and restarting the treatment will be at the trial physician's discretion, though it is suggested that if deemed necessary, consultation with the Sponsor may be done. Treatment re-initiation should occur as soon as possible and has to be confirmed by trial physician. Re-initiation of treatment will include a general safety examination by qualified medical personnel and safety labs. Restarting treatment after an interruption period that is greater than 10% of the trial length (i.e. 18 consecutive days) will be discussed between sponsor and trial physician before a final decision is made to re-initiate treatment at the discretion of the Sponsor. All information relating to interruption of treatment and re-initiation will be documented. Missed doses from the above category will not be considered in determining non-compliance.

7.5.1 Interruption of Treatment not related to short term treatment with excluded medication, hospitalization, personal circumstance or AE.

At the discretion of Principal Investigator, participants may request an interruption of treatment due to commitments such as travel obligations, for one block of time, up to 4 weeks in duration (28 dosage days). The study recording of interruption of treatment will allow for the addition of the time taken off to the study treatment period, up to the predetermined 28 dosage days. This interruption will not be factored into non-compliance, and a safety examination by study clinician is not required prior to resuming treatment.

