Common but non-life threatening side effects include:

- Fatigue or asthenia
- Malaise
- Rash
- Itching (pruritus)
- Vomiting
- Diarrhea
- Abdominal pain
- Sore throat (pharyngitis)
- Chills
- Bone pains
- Joint pains
- Weight loss or gain
- Elevations in kidney or liver enzymes
- Fluid retention (peripheral edema)
- Injection site irritation
- Insomnia
- Headaches
- Transient Fevers

Less common but potentially serious side effects include:

- Bleeding into the eye
- Allergic reactions
- Excessive increase in white blood cell count
- Fluid retention in the lung lining (pleura) and in the heart lining (pericardium)
- Shortness of breath
- Occasional transient heart rhythm changes (supraventricular tachycardia)
- Sweating, tachycardia, claustrophobia, or anxiety induced by the MRI procedure

Potential side effects of unknown frequency:

- Leukopenia (low white blood cell count)
- Neutropenia (low neutrophil count)

Adverse event of special interest (AESI) include:

An AESI is an AE (serious or non-serious) of scientific and medical concern specific to the program, for

which ongoing monitoring and immediate notification to the DSMB is required. Such events may require further investigation in order to characterize and understand them. Adverse events of special interest may be added or removed during a study by protocol amendment.

- ADA
- Acute hypersensitivity/anaphylaxis
- Leukopenia (low white blood cell count)
- Neutropenia (low neutrophil count)

Report of Unexpected Problems to the DSMB: The study coordinator will notify the PI or qualified sub-Investigator of any unexpected problems. The PI will contact the chair of the **DSMB** when unexpected problems arise that require immediate action.

Criteria for Action:

Specific triggers that will dictate when a specified action (such as reporting or stopping) is required. Any SAE or unexpected problem that meets the COMIRB criteria of reporting will be reported per COMIRB guidelines. Any serious AEs meeting the FDA reporting criteria, the FDA will also be notified according to their reporting guidelines.

Stopping rules:

Study: If treatment related serious AEs (SAEs) of Grade 3 or 4 occur in 20% of participants following sargramostim administration, the study will be stopped (Appendix F).

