Participant: For individual participants, the **PI or Sub-I** may discontinue any participant if they reach grade 3 or 4 in any category, if laboratory results indicate blast cell appearance, or if they worsen in any of the cognitive tests by more than two standard deviations than would be normally expected from someone at their baseline measurements, or if they have any values that have exceeded greater than two times upper limits of normal for any trial measures. Participants are, of course, free to withdraw from the study at any time for any or no reason.

Specific participant stopping criteria for Absolute Neutrophil (ANC) count values are as follows:

• If a participants Absolute Neutrophil Count (ANC) is less than 0.5x10E3/uL (500 cells per microliter) at any CBC with differential safety blood draw post randomization, the participant will be monitored for potential infections over the course of 1 week until another CBC with differential is completed. If the ANC value does not demonstrate improvement (returned to a value above 0.5x10E3/uL), administration of the study drug to the participant should be discontinued.

Participants will be followed-up according to the study procedures as specified in this protocol up to the scheduled date of study completion, or up to recovery or stabilization of any AE to be followed-up as specified in this protocol, whichever comes last. If possible, and after the permanent discontinuation of treatment, the participants will be assessed using the procedures normally planned for the EOT visit with the treatment/placebo, including, but not limited to, LP (if chosen), imaging assessments and cognitive assessments. All cases of permanent treatment discontinuation should be recorded after confirmation.

The PI may also determine that a trial participant should no longer remain in the trial if there is evidence of uncontrolled hypertension. For an individual who has consented to volunteer for the trial, meets inclusion criteria and is enrolled, then begins the treatment phase of the trial, but who subsequently is determined to exhibit uncontrolled hypertension for more than 2 weeks (14 treatment days), the DSMB will be notified, within accepted timeframe, adverse events reporting protocols will be followed, and the following criteria will be used to determine whether the participant needs to be removed from the trial:

Inclusion Screening Criteria for hypertension:

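### Does section 9.2.1 need to name the unit of analysis for its Wilcoxon test on toxicity grades, and a tolerability outcome?

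*Protocol*

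**What the plan says.** Section 9.2.1 describes the safety analysis as generally descriptive and framed on the participants in each arm. It then states "Safety will be assessed by measuring the toxicity grades of AEs", graded by CTCAE version 5, and "Differences in toxicity grades will be compared between treatments using a Wilcoxon test for ordered outcome". It gives no rule for the unit of analysis, for repeated AEs or for participants without an AE.

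Other sections bear on the point:

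- Section 4.5: "The primary hypothesis is that long-term administration of sargramostim (recombinant human GM-CSF) will be tolerated by and safe for use in participants". Neither the endpoint table there nor section 9.2.1 names a tolerability outcome as such.
- Section 4.4.2, on the pilot: "The only AEs reported have been mild expected reactions to sargramostim, including injection site reactions".
- Section 7.4: a raised eosinophil count is one ongoing AE until it resolves. "Once the AE is resolved, a subsequent occurrence of an absolute eosinophil" count at or above the critical value is then a new AE.
- Section 7.5: "All information relating to interruption of treatment and re-initiation will be documented". Section 8.4.5.3: "All cases of permanent treatment discontinuation should be recorded after confirmation".
- Section 8.4.5.3, study stopping rule: treatment-related serious AEs of Grade 3 or 4 that "occur in 20% of participants following sargramostim administration". Section 8.4.5.2 has a similar halt based on the first 14 participants.
- Section 9.3.1 promises a full SAP before database lock.

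**The concern.** The Wilcoxon test is the only test that section 9.2.1 names for the primary objective, and the sentence before it speaks of the grades of AEs. An analyst could take that at face value and use one row per AE. Two things would then go wrong.

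First, several AEs from one participant would count as independent. AEs are reviewed weekly for 24 weeks, so repeats are likely.

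Second, the comparison would be conditional on having an AE. The pilot reported mild reactions to the drug. More of these in the sargramostim arm would lower the average grade among its AEs, so a less comfortable drug could appear less toxic. For a trial whose primary aim is safety, that is the wrong direction in which to err.

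The missing tolerability outcome adds to the worry. Compliance cannot stand in for one, because section 7.6 leaves AE-driven dose reductions and withheld doses out of non-compliance.

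**Working it through.** The protocol gives no AE rate, grade mix, alpha or power for this test, so there is no stated figure to reproduce. What can be checked is how the two readings behave.

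**Worked example.** Arm sizes of 28 and 14 come from section 9.1. Assume that every participant has AEs of Grade 1, 1 and 2, and that one in seven also has a Grade 3 AE (4/28 and 2/14).

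- Placebo: 28 Grade 1, 14 Grade 2 and 2 Grade 3, 44 AEs in all. Mean grade = (28 + 28 + 6)/44 = 1.41.
- Sargramostim: 56, 28 and 4, 88 AEs in all. Mean grade = (56 + 56 + 12)/88 = 1.41.

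Let θ = P(sargramostim grade higher) + ½ P(tie). Now add three Grade 1 AEs to each sargramostim participant. The counts become 140, 28 and 4 (172 AEs), and the mean becomes (140 + 56 + 12)/172 = 1.21.

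θ = [28×28 + 4×42 + ½(140×28 + 28×14 + 4×2)]/(172×44) = (952 + 2160)/7568 = 0.411

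| Grade 1 AEs added per sargramostim participant | Per-AE θ | Per-AE p | Worst-grade θ | Worst-grade p |
|---|---|---|---|---|
| 0 | 0.500 | 1.0 | 0.500 | 1.0 |
| 1 | 0.456 | 0.285 | 0.500 | 1.0 |
| 2 | 0.429 | 0.062 | 0.500 | 1.0 |
| 3 | 0.411 | 0.012 | 0.500 | 1.0 |
| 5 | 0.388 | 0.0004 | 0.500 | 1.0 |

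**The direction depends on the grade of the excess.** Add one Grade 2 AE per sargramostim participant instead. The counts are 56, 56 and 4 (116 AEs).

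θ = [56×28 + 4×42 + ½(56×28 + 56×14 + 4×2)]/(116×44) = (1736 + 1180)/5104 = 0.571

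The per-AE test now points towards harm. If every AE in both arms were Grade 1, all pairs would tie and θ would stay at 0.500.

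**Simulation** (28 versus 14, two-sided 5%; AE rates, grade mixes and within-participant correlation all assumed):

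- Identical arms, latent correlation 0.2, Grade 1/2/3 mixes of 55/33/12, 80/16/4 and 90/8/2: the per-AE test rejects in 9–18% of trials at 4 AEs per person and 13–24% at 8. At about 2 AEs per person it rejects in 3–11%. With zero correlation it holds about 5%.
- Two extra Grade 1 AEs per sargramostim participant on a background of 6: significantly lower grades on sargramostim in 17–18% (90/8/2), 25–26% (80/16/4) and 45% (55/33/12) of trials, against 2.5% by chance in that direction. With milder backgrounds (95/4/1 and 98/1.5/0.5) the figures are about 13% and 10%.
- One or two extra Grade 2 AEs instead: significantly higher grades on sargramostim in 26–41% (55/33/12), 50–82% (80/16/4) and 68–95% (90/8/2), and lower in at most 4%.
- Worst grade per participant (0 if no AE): 4–6% rejections with the extra Grade 1 AEs. A separate null run, with a 70/23/6/1 mix of Grades 1 to 4 and correlations from 0 to 0.5, gave 4.5–5.2%.

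**Which reading the text supports.** The opening of section 9.2.1 refers to participants, and so do both halting rules. A two-sample Wilcoxon test needs independent units, and the units randomised are participants. Nothing in the protocol asks for one row per AE.

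**The case for a change.** The strongest case for a change is that the protocol fixed the variable and the test for its primary objective but left out what makes the test valid. AE severity is assessed event by event (section 8.4.5), so a per-AE data set is what the analyst will first see. The likely error would reassure falsely. In a variant of the worked example with a true Grade 3 excess (10/28 versus 2/14) and five extra Grade 1 AEs per sargramostim participant, the per-AE test still favours sargramostim (θ = 0.403, p = 0.003), while worst grade points to harm (θ = 0.607, p = 0.16). Wording that prevented this would cost two or three sentences.

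The arithmetic stands: a per-AE Wilcoxon test would be a poor analysis here. It is also true that worst grade barely registers an excess of mild AEs, so AE counts or incidence by arm belong beside it. What does not stand is the step from an unstated unit to a wrong plan. The participant-level reading is available and sound, and it fits the surrounding text better. Collapsing repeated AEs, scoring participants without one, and tabulating AE incidence, discontinuations, interruptions and dose reductions by arm are what a SAP normally sets out. The data for the tolerability tables are already collected under sections 7.5 and 8.4.5.3, and section 9.3 leaves room for comparing event proportions.

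**Conclusion.** No change to the protocol follows. This is a gap in detail that analysts fill sensibly: one value per participant for the test, with AE incidence and treatment discontinuations, interruptions and reductions tabulated by arm. On that reading the Wilcoxon test keeps its nominal level.

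On the per-AE reading the error could be large: false rejection in roughly 9–24% of null trials at 4 to 8 AEs per person, and a false signal of lower toxicity in 17–45% with two extra Grade 1 AEs per sargramostim participant. Those figures assume a within-participant correlation of 0.2 and a background with enough higher-grade AEs. The false signal also needs the excess to be Grade 1; a Grade 2 excess usually moves the test the other way. The protocol supplies none of these quantities.

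Even then, the consequence would be a misleading p-value beside descriptive safety tables. No success criterion and no stopping decision rests on it.
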